4.6.1.2 Presentation

Duration of exposure, actual duration of exposure, RDI, and treatment compliance will be summarised using descriptive statistics for continuous data and listed. Counts and percentages for the number of planned starting dose received, dose interruptions, reasons

for dose interruptions, dose reductions, reason for dose reductions, dose modifications (ie, dose interruption and/or dose reduction), and treatment compliance thresholds will be provided.

Treatment compliance percentage will be summarised as a continuous variable using descriptive statistics and by counts and percentages using the following categories:

CCI

CCI

CCI

Exposure and treatment compliance data will be presented by cohort and total.

Exposure data will be listed, including the date of first exposure to treatment, duration (intended) of exposure (days), actual duration of exposure (days), RDI, treatment compliance, and transition to capsule formulation.

4.6.2 Adverse Events

4.6.2.1 Definitions and Derivations

The MedDRA version 26.1 or higher is used to code AEs. AEs are graded according to the CTCAE version 5.0.

AEs will be collected from the time of signature of the ICF until 30 days after the last dose of selumetinib or 25 cycles of treatment, whichever is earlier. For participants taking part in the long-term safety follow-up (participants < 5 years of age), after 25 cycles of treatment or end of treatment, AEs causally related to selumetinib will be collected until they complete the study in accordance with CSP Table 3. The long-term safety follow-up is designed to assess the long-term safety of selumetinib treatment in participants who are < 3 years of age when they commence selumetinib, as there are no long-term safety data currently available for patients who received selumetinib at this age. No AEs will be collected for participants who are > 5 years of age who remain in the study after 25 cycles of treatment.

A treatment-emergent AE will be defined as an AE that starts, or worsens, after the first dose of selumetinib up to and including 30 days after the last dose of selumetinib.

AEs of special interest

Some clinical concepts (including some selected individual preferred terms and higher-level terms) have been considered AESIs to the selumetinib program.

The AESIs in [Table 16](#) have been identified as a list of categories by the patient safety team.

Table 16 **AEs of special interest**

AESI	MedDRA Preferred Terms Defining the AESIs
Ocular toxicity	Chorioretinopathy (central serous retinopathy [CSR]); Retinal detachment; Retinal tear; Vision blurred; Visual impairment; Vitreous floaters; Photopsia; Eye disorder; Photophobia; Retinal vein occlusion (RVO); Detachment of retinal pigment epithelium (Retinal pigment epithelial detachment [RPED]).
Hepatotoxicity	Drug-induced liver injury; ALT increased; AST increased.
Muscular toxicity	Blood creatine phosphokinase increased; Musculoskeletal pain; Muscular weakness; Myalgia; Rhabdomyolysis; Myoglobin blood increased; Myoglobin urine present; Acute kidney injury; Myopathy.
Cardiac toxicity	Ejection fraction decreased; Oedema peripheral; Peripheral swelling; Oedema; Left ventricular dysfunction; Ventricular dysfunction.
Physeal dysplasia	Metaphyseal dysplasia; Multiple epiphyseal dysplasia; Arthralgia; Joint stiffness; Joint hyperextension; Gait disturbance; Short stature.
Choking on the capsule	Choking; Retching.

AESI, adverse event of special interest; MedDRA, Medical Dictionary for Regulatory Activities.

Other significant adverse events

During the evaluation of the AE data, an AstraZeneca medically qualified expert will review the list of AEs that were not reported as SAEs and AEs leading to discontinuation. Based on the expert's judgement, significant AEs of particular clinical importance may, after consultation with the Global Patient Safety Physician, be considered OAEs and reported as such in the CSR.

A similar review of laboratory/vital signs/ECG data will be performed for identification of OAEs. Examples of these could be marked haematological and other laboratory abnormalities, and certain events that lead to intervention (other than those already classified as serious), dose reduction or significant additional treatment.

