a. After 25 cycles (or discontinuation of selumetinib) participants who are aged < 5 years will enter a long term safety follow-up and assessments will be performed as per Table 3. After 25 cycles of treatment if participants are > 5 years of age and unable to access commercial supply and are still receiving clinical benefit participants may be able to remain on treatment in the study. Assessments will revert to standard of care at the particular site. There will be no more data collection except SAE, overdose and pregnancy reporting. All SAEs, overdoses and pregnancies will be reported until 30 days after last dose.

b. Once participants attain a BSA between 1.10 and 1.29 m^2 they will be encouraged to completely transition to the capsule formulation, if feasible, although all participants must remain on the granule formulation until after they have completed their third cycle of treatment.

c. An EoT visit will be performed for participants who permanently discontinue study intervention for any reason (except for death, lost to follow-up, or withdrawal of consent). The EoT visit should be performed as soon as possible after the end of treatment.

d. Calculation of BSA should be done at the specified time points but since BSA determines the dose of selumetinib it should also be calculated more frequently, as appropriate, depending on the age and growth rate of the child.

e. Assessment of baseline disease characteristics includes documenting location of the target and non-target PN (if applicable), any PN-related symptoms and results of any previous genetic testing for NF1. (Participants recruited under CSP Version 1.0 will have this data entered in the EDC if available retrospectively.)

- f If clinical safety laboratory assessments, urinalysis and performance status have been done within 14 days of starting study intervention they do not need to be repeated on C1D1 if the participant's condition has not changed. If laboratory procedures were performed for alternate reasons prior to signing consent (but within the 28 day screening window), these can be used for screening purposes with consent of the legally authorised representative (parent or guardian) of the participant.

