- x. Adverse events will be collected from the time of signing the informed consent form, throughout the treatment period, and including the follow-up period.
- y. Other systemic NF1-PN targeted treatments will be collected for all participants who discontinue selumetinib until the time when they would have completed 25 cycles of treatment, or they commence an alternative systemic NF1-PN treatment whichever is the earliest.
- z. Consent can be performed on Day -42 onwards. All screening assessments must be performed within 28 days prior to dosing.

CCI	; BSA, body surface area; C, cycle; CSP, Clinical Study Protocol;
D, day; CCI	; ECG, electrocardiogram; EDC, electronic data capture; EoT, end of treatment; CC
CCI	; FU, follow-up; CCI
CCI	LLN, lower limit of normal; LVEF, left ventricular ejection fraction; MRI, magnetic resonance imaging; NF1, neurofibromatosis
type 1; PD, pharmacodynamic	: CC : PK, pharmacokinetic(s): PN, plexiform neurofibroma: SoC, standard of care;

VMI, Visual-Motor Integration; W, week.

AstraZeneca

	Participants receiving selumetinib treatment a			Participants no longer receiving selumetinib treatment		
Procedure b	Every 6 cycles	Every 12 cycles	EoT Safety Follow-up (30 days after last dose)	Every 6 months	Every year	Section or Appendix
Window	±7 days	±7 days	+ 7 days	± 7 days	±7 days	
Full Physical examination	Х		X	Х		8.3.1
Height, weight	Х		X	Х		8.3.2
BSA	Х			Х		8.3.2
Clinical safety laboratory assessments	Х		X	Х		8.3.9
12-lead ECG	Х		Х	If clinically	y indicated	8.3.4
Echocardiogram	Approximately	every 3 cycles	Х	If clinically indicated		8.3.5
Ophthalmology examination		X	Х	If clinically	y indicated	8.3.6
Knee MRI/X-ray (Physeal dysplasia)		X			Х	8.3.7
Performance status	Х		Х	Х		8.3.8
Urinalysis	Х		Х	Х		8.3.9
Vital signs	Х		Х	Х		8.3.3
CI	1	1				
Dispense medication d	To be dispensed	l every 2 cycles				6
Return Medication/Compliance Check		>	Х			6.2 6.4
SAEs and AEs causally related to selumetinib	←======	→	Х	← =======	→	8.4

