### Table 3Schedule of Activities – Safety Follow-up until Participants are aged 5 Years

a. PN tumour assessment should be continued as standard of care if participants remain on treatment. No information about the MRI will be collected (i.e., not date/time of scan or images).

b. The participant should continue to attend all assessments as described until they are  $\geq$  5 years of age (assessments should continue until the first visit after their 5th birthday) or commence an alternative systemic NF1-PN targeted treatment, whichever is earlier.

CCI

Selumetinib will be dispensed every 2 cycles ( $\pm$  3 days). If feasible, site to participant transport of study drug will be utilised.

AE, adverse event; BSA, body surface area; ECG, electrocardiogram; EoT, end of treatment; MRI, magnetic resonance imaging; NF1, neurofibromatosis type 1; PN, plexiform neurofibroma; SAE, serious adverse event.

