Participants who are aged  $\geq$  5 years at the end of 25 cycles of selumetinib will be considered to have completed the study for data analysis purposes. Participants who terminate treatment prior to Cycle 25 will be followed up to collect MRIs performed as standard of care, and details of NF1-PN treatment information until the time when they would have completed 25 cycles of treatment, or they commence an alternative systemic NF1-PN treatment, whichever is the earliest. Any participant who is aged < 5 years after 25 cycles of selumetinib (or when they terminate treatment with selumetinib) will enter a safety follow-up phase until they reach the age of 5 years or commence an alternative systemic NF1-PN treatment, whichever is the earlier. Participants can continue to receive selumetinib (capsule or granule formulations) during the safety follow-up as long as they are considered to be receiving benefit in the opinion of their Investigator. The safety follow-up is designed to assess long term safety of selumetinib treatment in participants who are < 3 CONFIDENTIAL AND PROPRIETARY 40 of 168 Clinical Study Protocol -5.0 Astra Selumetinib - D1346C00004 years of age when they commence selumetinib as there are no long term safety data currently available for patients who received selumetinib at this age.

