# 8.4.1 Time Period and Frequency for Collecting AE and SAE Information

Adverse events will be collected from the time of signature of the ICF until 30 days after the last dose of selumetinib or 25 cycles of treatment, whichever is earlier. For participants taking part in the long term safety follow-up (participants < 5 years of age), after 25 cycles of treatment or end of treatment, adverse events causally related to selumetinib will be collected until they complete the study in accordance with Table 3. No AEs will be collected for participants who are > 5 years of age who remain in the study after 25 cycles of treatment.

SAEs will be collected from time of signing the ICF throughout a subject's participation in the study.

If the Investigator becomes aware of an SAE with a suspected causal relationship to the IMP that occurs after the end of the clinical study in a participant treated by him or her, the Investigator shall, without undue delay, report the SAE to the Sponsor.

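### The treatment-emergent window has no Cycle 25 limit, so any-causality AE rows at DCO2 mix complete and related-only capture for children under 5 who stay on selumetinib

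*SAP*

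**What the plan says.** **Collection.** Protocol 8.4.1 collects AEs of any cause from consent "until 30 days after the last dose of selumetinib or 25 cycles of treatment, whichever is earlier"; SAP 4.6.2.1 repeats the rule. For children under 5 in the long-term follow-up, after 25 cycles or end of treatment, "adverse events causally related to selumetinib will be collected until they complete the study in accordance with Table 3". SAEs are collected throughout participation. Protocol Table 3 has one event row, "SAEs and AEs causally related to selumetinib", and it applies to children still on treatment as well as to those who have stopped.

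**Dosing.** Protocol 4.1.2: "Participants can continue to receive selumetinib (capsule or granule formulations) during the safety follow-up", for as long as the investigator sees benefit. Table 3 footnote b adds that "assessments should continue until the first visit after their 5th birthday".

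**Analysis window.** SAP 4.6.2.1 counts as treatment-emergent "an AE that starts, or worsens, after the first dose of selumetinib up to and including 30 days after the last dose of selumetinib". Protocol 9.4.3.1 says treatment-emergent AEs are what is summarised, and its own definition has no end date.

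**Data used.** SAP 4.6 presents off-treatment follow-up data separately and is silent on on-treatment data after Cycle 25. SAP 4 uses all available data at DCO2. Under SAP 3.1, DCO2 waits until every participant has had the chance to complete 25 cycles or has stopped.

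**The concern.** The rule for recording AEs changes at Cycle 25, but the rule for counting them does not. For a child under 5 who stays on drug, an unrelated non-serious event in Cycle 20 is recorded and counted. The same event in Cycle 30 falls inside the treatment-emergent window but is never recorded. Both periods feed one percentage, and SAP 3.3 takes percentages over the population total, so nothing adjusts for the incomplete period.

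The SAP 4.6.2.2 rows exposed are those that can include unrelated non-serious events:

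- all AEs, grade 3 or higher, and maximum grade;
- AESIs and other significant AEs;
- non-serious AEs above the 5% threshold;
- AEs leading to discontinuation, interruption or reduction.

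The last group belongs on the list. Protocol 6.6 foresees interruptions for unrelated AEs, and 7.1 allows discontinuation for any AE judged to contraindicate dosing. The route is narrowest for reductions, which 6.6 ties to AEs at least partly related.

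The follow-up exists to describe long-term safety in children who start under 3, and these are the children affected. In the listed rows their percentages would describe neither the first 25 cycles nor the whole time on drug, and the error is towards apparent safety.

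**Working it through.** The plan gives no figure to reproduce, so the check is calendar arithmetic on the two windows.

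**Inputs from the documents.** The cycle is 28 days (protocol 4.1.2). This reproduces the schedule in Table 2: Cycle 25 Day 1 falls in week 24 × 4 + 1 = 97.

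**Who is affected.** The end of Cycle 25 is 25 × 28 = 700 days = 700/365.25 = 1.916 years. A child is still under 5 then if entry was before 5 − 1.916 = 3.08 years. That is most of the Cohort 2 age range and the youngest of the Japan Cohort. SAP 3.4 requires at least 3 children under 2, who are at most about 3.92 years old at day 700.

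**Why it arises at DCO2.** The last participant sets the date, so earlier entrants can be past Cycle 25. Staggered entry is built in: protocol 6.1.2 pauses further Cohort 2 dosing while the first 3 evaluable children are reviewed.

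**Share of on-treatment time under related-only capture at DCO2.** Let g be the time in years by which a child entered before the last participant (assumed; not given). With continuous dosing, the share is g/(1.916 + g).

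- g = 0.5: 0.5/2.416 = 21%. The child stays under 5 throughout if entry was before 5 − 2.416 = 2.58 years.
- g = 1: 1/2.916 = 34%. Entry before 5 − 2.916 = 2.08 years.

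**Effect on a tabulated percentage.** For a non-serious event at constant rate λ per year, with a fraction r judged related (both assumed):

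- tabulated = 1 − exp[−λ(1.916 + r·g)]
- complete capture = 1 − exp[−λ(1.916 + g)]
- first 25 cycles only = 1 − exp[−λ × 1.916]

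| λ | g | First 25 cycles | Tabulated, r = 0.25 to 0.75 | Complete capture |
|---|---|---|---|---|
| 0.1 | 0.5 | 17.4% | 18.5% to 20.5% | 21.5% |
| 0.1 | 1 | 17.4% | 19.5% to 23.4% | 25.3% |
| 0.5 | 0.5 | 61.6% | 64.0% to 68.2% | 70.1% |
| 0.5 | 1 | 61.6% | 66.2% to 73.6% | 76.7% |

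At λ = 0.1 the shortfall is 1.0 to 3.0 points (6 months) or 1.9 to 5.8 points (12 months), among affected children only. In a whole-cohort row it is multiplied by the fraction of children affected, which is unknown.

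**DCO1.** The last participant need only have had time for 3 cycles. To be past Cycle 25, a child would have to have entered more than 22 cycles (22 × 28 = 616 days) earlier.

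**The case against.** The case for leaving the plan alone is that safety is descriptive, DCO1 is the primary safety analysis, all AEs are listed, DCO3 already presents the under-5 subset, and no SAP wording recovers events that were never collected. Each of these is correct, and together they limit the importance of the point. They do not remove it. A listing cannot show events that were not recorded, and no passage caps the window or separates on-treatment events after Cycle 25.

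A reader might also infer more than the documents support:

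- **That SAE or related-AE counts are incomplete.** SAEs are collected throughout, and related AEs continue to be collected in children under 5, so each of those rows follows one rule. Nor does curing the defect require cutting them at Cycle 25, which would move fully captured later SAEs out of view.
- **That about half of on-treatment time lacks complete capture.** For a child starting at age 1 and dosed to 5, complete capture covers 1.916/4 = 48%. That is a full-follow-up picture. It suits a cumulative DCO3, not DCO2, and SAP 3.1 and 4 do not settle whether DCO3 tables are cumulative.
- **That protocol 8.4.13 conflicts with 8.4.1 by requiring all AESIs after Cycle 25.** The sentence in 8.4.13 mainly concerns how quickly AESIs are recorded; 8.4.1 sets the collection period.
- **That children aged 5 or over raise the same problem.** Protocol 4.1.2 says those aged 5 or over at the end of 25 cycles "will be considered to have completed the study for data analysis purposes", and Table 2 footnote a says of those who remain on treatment: "There will be no more data collection except SAE, overdose and pregnancy reporting". This largely settles it.

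**Conclusion.** The point holds for DCO2 and should be corrected. Followed as written, the SAP puts incompletely captured time into any-causality AE rows, so those rows understate incidence over the window they claim to cover. The same applies at DCO3 if its tables are cumulative. If DCO3 showed only data after DCO2, an on-treatment all-AE row would be mislabelled rather than mixed.

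The size is modest and uncertain: a few percentage points among affected children for an uncommon event, more for a common one or a longer entry gap, and less in whole-cohort rows. It rests on assumed entry gaps, a constant event rate, an assumed related fraction, continuous dosing, and the child remaining under 5. How many children stay on drug past Cycle 25 is not given; if none do, the effect is nil.

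**What to change.** In SAP 4.6.2:

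1. End the any-causality AE rows at the earlier of last dose plus 30 days and the last day of Cycle 25.
2. Keep SAE and possibly-related rows available over the full on-treatment window, with the period footnoted or in their own labelled table, so that the overall summary is not misread as covering one period.
3. Add one table of on-treatment events after Cycle 25 in children under 5, labelled as SAEs and related AEs only, with the exposure time it covers.
4. State whether DCO3 tables are cumulative.

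Separately, reconcile the earlier-of rule in protocol 8.4.1 and SAP 4.6.2.1 with Table 2, which marks AE collection at the 30-day follow-up visit and whose footnote x includes the follow-up period. Read literally, the rule leaves out those 30 days for a child who stops at the end of Cycle 25.

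The cost is SAP wording, a clarification in protocol 8.4.1, one date flag and one extra table set; no new visits or data. SAP 3.3.3 already cuts on-treatment MRI at the last day of Cycle 25, so the device is familiar. The any-causality percentages will be lower than under the mixed window, and uncollected events are not recovered.

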4.6.2.2 Presentation

Summary tables of the number and percentage of participants with AEs by system organ class and preferred term will be produced for below categories. The number and percentage of participants with AESIs will be summarised by AESI grouped term and preferred term. An overall summary table will include the number and percentage of participants in each category.

- All AEs
- AEs possibly related to study intervention
- AEs of CTCAE grade 3 or higher
- AEs with CTCAE grade 3 or higher, possibly related to study intervention
- SAEs with an outcome of death
- SAEs with outcome of death possibly related to intervention
- All SAEs
- SAEs possibly related to study intervention
- AEs leading to discontinuation of study intervention
- AEs leading to discontinuation of study intervention, possibly related to study intervention
- AEs leading to dose interruption and reduction (separately)
- AESIs
- OAEs

The number of subjects and events will also be presented for non-serious AEs occurring in more than 5% of participants.

CTCAE grades and summaries of the number and percentage of participants will be provided by system organ class, preferred term and maximum reported CTCAE grade.

All AEs, SAEs, AESIs, AEs with outcome of death, AEs leading to treatment discontinuation, and AEs occurring > 30 days after last dose of selumetinib will be listed in the same subject listing.

All AEs listings will include the formulation (granule or capsule) variable at the event start date of the event.

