# **3 OBJECTIVES AND ENDPOINTS**

The objectives and endpoints of the study are shown in Table 5.

Objectives	Endpoints		
Primary			
• To determine the PK of selumetinib after administration of the selumetinib granule formulation.	• Selumetinib AUC0-12 derived after single dose administration.		
• To assess the safety and tolerability of the selumetinib granule formulation.	
 
Safety and tolerability will be evaluated in terms of AEs, clinical safety laboratory assessments (clinical chemistry, haematology, urinalysis), physical examination, weight, vital signs, ECG, ECHO, ophthalmologic assessment, knee (or wrist) MRI/X-ray, and performance status.
 
Assessments related to AEs will include: occurrence/frequency; relationship to study intervention; CTCAE grade; seriousness; death; AEs leading to discontinuation of study intervention; AEs of special interest.
 
		
Secondary			
• To assess the palatability of the selumetinib granule formulation	• Palatability will be assessed using the parent-reported observer palatability assessment.		
To further assess the PK of selumetinib and N-desmethyl selumetinib metabolite after administration of the selumetinib granule formulation.	
 
Plasma concentrations and PK parameters of selumetinib including, but not limited to:         
 
Selumetinib AUC0-12 derived after multiple dose administration.
 
Cmax, AUC0-6, AUClast, CL/F, tmax, tlast derived after single and multiple dose administration.
 
AUC0-24, Vz/F and t½λz after single dose administration.
 
AUC0-24, Vz/F and t½λz after single dose administration.
 
Rac Cmax, Rac AUC0-12, and Vss/F derived after multiple dose administration.
 
 
 
Plasma concentrations and PK parameters of N-desmethyl selumetinib including, but not limited to:         
 
Cmax, AUC0-6, AUC0-12, AUClast, tmax, tlast derived after single and multiple dose administration.
 
Rac Cmax and Rac AUC0-12 derived after multiple dose administration.
 
 
 
Parent-to-metabolite ratio for AUC0-6, AUC0-6, AUC0-12 and AUC0-24 (single dose only), and Cmax after single and multiple dose administration.
 
		
• To evaluate the efficacy of the selumetinib granule formulation by assessment of ORR as determined by ICR per REiNS criteria.	Objective Response Rate		
Endpoints			
--			
CCI     CCI     CCI     CCI     CCI      CCI			
Parent-reported CCI     total score.			
• CCI			

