a. In the rare circumstance that a participant is unable to transition to capsule selumetinib when they attain a BSA between 1.10 and 1.29 m^2 participants can continue to receive the granule formulation at the dose shown in Table 8.

Note that only one dose of selumetinib will be taken on C1D1; bid dosing will start on C1D2. bid, twice daily; BSA, body surface area; C, cycle; D, day.

At enrolment participants must have a BSA within the range 0.40 to 1.09 m^2. Once participants attain a BSA between 1.10 and 1.29 m^2 they will be encouraged to completely transition to the capsule formulation, if feasible, although all participants must remain on the granule formulation until after they have completed their third cycle of treatment. Upon transition to the capsule formulation, PK sampling should be performed on Day 7 (range Day 4 to 14) as long as the participant has received 3 consecutive days of twice daily dosing with capsule formulation immediately prior to the PK day, see Section 8.6.1.1 for more details. The dosing schedule for the capsule formulation is shown in Table 8.

BSA (m  )	Capsule Dose (bid approximately 12 hours apart)	Dose level (mg/m  )
$1.10 - 1.29 \text{ m}^2$	30 mg	23.3 - 27.3
1.30-1.49 m 	35 mg	23.5 - 26.9
1.50-1.69 m 	40 mg	23.7 - 26.7
1.70-1.89 m 	45 mg	23.8 - 26.5
$\geq$ 1.90 m 	50 mg	20.0 - 26.5

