3.2.3 Safety Analysis Set

All participants who received at least one dose of selumetinib.

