4.2 Endpoint Analyses

This section covers details related to the endpoint analyses such as primary, secondary, and other endpoints including sensitivity and supportive analyses.

The CCI [REDACTED] and CCI [REDACTED] analyses will not form part of the clinical study report and will not be handled by the statistical and programming vendor. The CCI [REDACTED] and CCI [REDACTED] analyses will be analysed and presented separately from the main clinical study report. Thus, they are outside the scope of this SAP.

Statistical category	Endpoint	Population	Population level summary (analysis)	Details in section
To determine the PK of selumetinib after administration of the selumetinib granule formulation				
Primary	Selumetinib AUC0-12 derived after single dose administration	PK	Descriptive statistics	4.4
To assess the safety and tolerability of the selumetinib granule formulation				
Primary	AEs, AESIs and SAEs. Duration of exposure and treatment compliance percentage. Absolute values and changes from baseline in Laboratory assessments. Vital signs, ECG, ECHO, ophthalmologic assessment, Knee (or wrist) MRI/X ray, and performance status.	Safety	Descriptive statistics	4.6
To assess the palatability of the selumetinib granule formulation				
Secondary	Palatability will be assessed using the parent-reported observer palatability assessment.	Safety	Descriptive statistics	4.2.3
To further assess the PK of selumetinib and N-desmethyl selumetinib metabolite after administration of the selumetinib granule formulation				

Statistical category	Endpoint	Population	Population level summary (analysis)	Details in section
Secondary	Single and multiple dose plasma concentrations and PK parameters of selumetinib and N-desmethyl selumetinib (see Section 4.4 for list of parameters).	PK	Descriptive statistics	4.4
To evaluate the efficacy of the selumetinib granule formulation by assessment of ORR as determined by ICR per REiNS criteria				
Secondary	ORR Safety ORR estimate and	4.2.5	two-sided 95% CI based on the exact CCI	

To evaluate the efficacy of the selumetinib granule formulation by assessment of CCI [REDACTED] and CCI as determined by ICR per REiNS criteria				
Exploratory	CCI [REDACTED]	Participants who have a CCI [REDACTED] in safety	CCI [REDACTED] CCI [REDACTED] CCI [REDACTED] CCI [REDACTED]	4.2.6
Exploratory	CCI [REDACTED]	Safety	CCI [REDACTED] [REDACTED]	4.2.7
Exploratory	CCI [REDACTED]	Safety	CCI [REDACTED] CCI [REDACTED]	4.2.8

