4.6.1 Exposure and treatment compliance

4.6.1.1 Definitions and Derivations

Duration of exposure will be defined as follows:

- Duration of exposure = last dose date where dose > 0 mg – first dose date + 1 (if last dose date is missing the earliest date between DCO, date of death and treatment discontinuation date will be used).
- Actual duration of exposure = duration of exposure – total duration of dose interruptions, where duration of exposure will be calculated as above, and a dose interruption is defined as any days with dose = 0 mg and half days if planned frequency is twice per day, but actual frequency is once daily only

This calculation will use the individual start and stop dates and the study intervention dosing frequency on the EX form of the CRF, which will account for any dose interruptions. The actual duration of exposure calculation makes no adjustment for any dose reductions that may have occurred.

Participants who permanently discontinue during a dose interruption

If a participant permanently discontinues study intervention during a dose interruption, then the date of last administration of study medication will be used in the calculation of exposure. In this case, the interruption would not be included in the summary tables, but it will be included in the listings.

Relative dose intensity

RDI is the percentage of the actual dose delivered relative to the intended dose through to study intervention discontinuation. RDI will be defined as follows:

- $RDI = 100\% * d/D$, where d is the actual cumulative dose delivered up to the actual last day of dosing and D is the intended cumulative dose up to the day of treatment discontinuation or actual last day of dosing. D is the total dose that would be delivered if the participant received the planned dose as per the CRF.

Intended cumulative dose is calculated by summing all the individual doses that should have been taken up to and including the last day of treatment according to the protocol planned dose and schedule. This is defined as follows:

Integer part (rounded up) of $[(\min(\text{date of last dose date where dose} > 0, \text{date of death, date of DCO}) - \text{first dose date} + 1) \times \text{intended dose according to the protocol}] / 0.5$
The intended dose of selumetinib is $\text{[REDACTED]} \text{ mg/m}^2$ twice daily.

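### Adverse event and exposure summaries pool granule and capsule dosing, although the primary safety objective is about the granule formulation

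*SAP*

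**What the plan says.** Protocol section 3 gives the primary safety objective as "To assess the safety and tolerability of the selumetinib granule formulation". SAP section 4.2 repeats that objective and puts these variables first under it: "AEs, AESIs and SAEs. Duration of exposure and treatment compliance percentage".

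Treatment is planned for 25 cycles. Entry is capped at a BSA of 1.09 m². Once children reach 1.10 to 1.29 m², Protocol section 6.1.1 says "they will be encouraged to completely transition to the capsule formulation, if feasible", but not before the third cycle is complete.

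On reporting, SAP section 4.6.1.2 says "Exposure and treatment compliance data will be presented by cohort and total", and puts the transition to capsules in the exposure listing. SAP section 4.6.2.2 lays out AE tables by system organ class, preferred term and maximum grade, with AESIs by grouped term. It brings in formulation only for listings: "All AEs listings will include the formulation (granule or capsule) variable at the event start date of the event". SAP section 4.1.1.1 adds a disposition count of children who switched.

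**The concern.** The objective names one product, while the summaries that answer it describe whichever product the child was taking. That would matter little if the two were interchangeable for safety, but the documents separate them in four ways:

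- **Food.** Capsules are taken fasted at every dose. Granules need fasting only on intensive PK days, and only from age 4 (Protocol 6.1.1).
- **Excipient.** Capsules contain a vitamin E compound, up to about 261.6 mg of vitamin E a day. Supplemental vitamin E is barred on capsules and allowed on granules (Protocol 6.5).
- **Peak concentration.** In healthy adults the granule to capsule ratio for dose-normalised Cmax was 0.654 (90% CI 0.581 to 0.736) (Protocol 2.1).
- **Swallowing.** One AESI category is choking on the capsule, made up of choking and retching (SAP 4.6.2.1). A pooled count cannot show which product was in use.

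The pooled tables therefore describe selumetinib in children who started on granules. A reader of the study report could take every event, dose reduction and treatment day in them as granule experience.

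**Working it through.** The plan gives no number of switchers and no capsule share of exposure, so there is no planned figure to reproduce. The check has two parts.

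**1. Does anything between the objective and the tables restrict to granules?**

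- Population (SAP 3.2.3): "All participants who received at least one dose of selumetinib". Either formulation qualifies.
- Treatment-emergent window (SAP 4.6.2.1): "after the first dose of selumetinib up to and including 30 days after the last dose of selumetinib". It runs through the switch.
- Duration of exposure (SAP 4.6.1.1): counted from the first dose to the "last dose date where dose > 0 mg". It also runs through the switch.
- Data included (SAP 4): all available data at DCO1 and DCO2, with no cut at Cycle 3 or at transition.
- Table columns (SAP 4): Global Cohort 1, Global Cohort 2, Global combined, Japan and all participants. Formulation is not a column.
- Sensitivity or supplementary safety tables limited to granule dosing: none.

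By contrast, PK is summarised by formulation (Protocol 9.4.2.2), and palatability is no longer expected after transition (SAP 3.3.9). The gap is in the safety summaries.

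**2. How large could it be?**

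Inputs: 28-day cycles and 25 planned cycles (Protocol 1.1 and 1.3), with the earliest switch after Cycle 3. As a check on cycle length, Cycle 25 Day 1 falls in week (25 − 1) × 4 + 1 = 97, which agrees with the schedule of activities.

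For one child, planned days are 25 × 28 = 700 and the minimum granule days are 3 × 28 = 84. The maximum capsule days are 700 − 84 = 616, and 616/700 = 22/25 = 88%.

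For the study, suppose a share *p* of children switch after cycle *s* and all complete 25 cycles. The capsule share of pooled days is *p* × (25 − *s*)/25. The values of *p* and *s* are assumptions.

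| Share switching | Switch after Cycle 3 | After Cycle 12 | After Cycle 18 |
|---|---|---|---|
| 5% | 4.4% | 2.6% | 1.4% |
| 10% | 8.8% | 5.2% | 2.8% |
| 20% | 17.6% | 10.4% | 5.6% |
| 30% | 26.4% | 15.6% | 8.4% |

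Worked example at 10%: 0.10 × 22/25 = 8.8% and 0.10 × 7/25 = 2.8%.

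**The case against.** The other side has several good points.

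**The primary safety analysis is largely protected.** DCO1 is timed to the opportunity to complete three cycles, and those cycles are granule-only by rule. This stands. Capsule data reach DCO1 only through earlier enrollees who have passed Cycle 3 and already switched.

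**The 88% child is an outlier.** Under the Mosteller formula (Protocol 8.3.2), a BSA of 1.09 m² needs weight × height = 1.09² × 3600 ≈ 4277. At 27 kg that means about 158 cm; at an assumed 125 cm it means about 34 kg. Protocol 8.6.2 describes a 6-year-old of 27 kg as already near the 98th percentile. Switches later in the 25 cycles are more plausible, and they carry less capsule time. This stands too.

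**Dosing does not change with the switch itself.** A reader might infer that the capsule dose and reduction tables set the two periods apart. The footnotes to Protocol Tables 7 and 10 send a child who stays on granules at 1.10 to 1.29 m² to the same Tables 8 and 11, so in that range the inference fails. The case rests on food, excipient, Cmax and swallowing. Even there, the adult dose-normalised AUC ratio is closer to one, at 0.865.

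**No cohort comparison is at risk.** Switchers are likely to be the larger, older children, so a reader might infer that Cohort 1 versus Cohort 2 is confounded by formulation. No hypotheses are tested and safety is descriptive only, so there is no planned comparison to bias.

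**The listings already allow a split.** They do, and for two choking-related terms in a small study that may be enough to read by eye. It is not a pre-specified summary for a primary objective.

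**Cutting at the switch has its own bias.** A display that stops at the first capsule dose would drop events that surface soon afterwards and late effects of granule dosing, such as growth-plate changes or falls in LVEF. This is a sound reason to keep the pooled tables, and to state how events near the switch are assigned.

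**Conclusion.** The point holds as a gap in presentation. The safety set, the treatment-emergent window, the exposure definition and the table columns all ignore formulation, so post-switch events and days are summarised under an objective that names granules.

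Its size is uncertain and probably modest. The documents do not state the number of switchers; the entry cap and the BSA threshold suggest a minority. At an assumed 10% switching with full follow-up, about 3% to 9% of pooled days would be capsule days. The 88% figure is a bound for one child followed for all 25 cycles and says nothing about the study as a whole. The effect is small at DCO1 and larger at DCO2, which is the analysis labelled as safety and efficacy of the granule formulation.

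A reader might also infer that the pooled tables are wrong and should be replaced. The documents do not support that: an any-dose safety set is pre-specified in the protocol, and whole-treatment reporting catches delayed effects. What is missing is a summary specific to granules beside it.

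**What to change.** In SAP sections 4.6.1.2 and 4.6.2.2:

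- Keep the pooled whole-selumetinib tables as planned.
- Add pre-specified summaries by formulation, with a granule-period and a capsule-period column, for AEs, AESIs, dose interruptions and reductions, and duration of exposure. Assign events by formulation at onset and split days at the transition date.
- State a carry-over rule for events ongoing at the switch or starting soon after it. One option is to flag events that start within 30 days of the last granule dose, in line with the existing treatment-emergent window, and to show the granule column with and without them.
- State that conclusions about granule safety will rest on the granule-period column, read alongside the pooled table.

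Formulation at onset and transition information are already planned for the listings, so this needs SAP wording and a few table shells, with no new data or visits. The drawback is small counts in the capsule column, which should be presented descriptively and not over-read.
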